Study Protocol and Statistical Analysis Plan

Title: Sulforaphane Treatment of Children with Autism Spectrum Disorder (ASD).

NCT: *NCT02561481*

Document Date: *11/28/2016, most recently approved by IRB 07/03/2019*

1) **Title**

Sulforaphane Treatment of Children with Autism Spectrum Disorder (ASD).

2) **IRB Review History***

NA

3) **Objectives***

We propose to conduct a phase I/II, randomized, double blind, placebo-controlled, one-arm crossover clinical trial to test the safety and efficacy of orally administered sulforaphane in young boys and girls with autism.

Our *long term research goal* is to discover and develop pharmaceuticals of low toxicity that treat core cellular mechanisms underlying behavioral features of ASD. Our *objective* in this application is to define the clinical effects of sulforaphane in children with ASD, along with the biomarkers and cellular mechanisms that may explain these effects.

Our *specific aims are:*

1. To determine if there are measurable effects on social responsiveness and problem behaviors during treatment with orally administered Sulforaphane-rich Broccoli Seed Powder (referred to as sulforaphane hereafter) in 3-12 year old boys and girls with ASD. Our *working hypothesis*, based on strong preliminary data from our recent trial of sulforaphane in young adults with ASD, is that sulforaphane will have similar and measurably greater clinical effects in children with ASD;

2. To determine if treatment with sulforaphane is safe and well tolerated. Our *working hypothesis*, based on our previous work and other studies, is that there will be few or no signs of toxicity;

3. To elucidate cellular biomarkers that support the hypothesized mechanism of action of sulforaphane in ASD. Our *working hypothesis* is that sulforaphane will increase levels of Nuclear factor-erythroid factor 2 (Nrf2), improve antioxidant capacity, upregulate expression of heat shock proteins, and modify mTOR signaling pathways and cytokine expression.

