
Pharmacy at dose specific for child, dispense but hold before starting until review of clinical lab studies, then call to start medication.
 
7-week visit: Review progress; Perform CGI-I; ABC and SRS by parents; physical exam; phlebotomy/urine for clinical and research lab studies. Dispense BSP.
 
15-week visit: Review progress; Perform CGI-I; ABC and SRS by parents; physical exam; phlebotomy/urine for clinical and research lab studies. Dispense BSP.
 
22-week visit: Review progress; Perform CGI-I; ABC and SRS by parents; physical exam; phlebotomy/urine for clinical and research lab studies. Dispense BSP.
 
30-week visit: Review progress; Perform CGI-I; ABC and SRS by parents; physical exam; phlebotomy/urine for clinical and research lab studies. Discontinue medication
 
36-week visit: Review progress; Perform CGI-I; ABC and SRS by parents; physical exam; phlebotomy/urine for research lab studies. Record exit comments on study.
		
Task 5: Data storage and analysis	0-36 mo.	
SPECIFIC AIM 3: To elucidate cellular biomarkers that support the hypothesized mechanism of action of sulforaphane in ASD. Blood and urine samples will be collected at UMass in Pilot and Main clinical trial, processed, stored and shipped on dry ice to JH		
Task 1: Labwork at JH for Pilot Study of biomarkers: Nrf2, oxidative stress markers, heat shock proteins, mitochondrial functions, mTOR, cytokine	3-6 mo.	3-6 mo.
Task 2: Labwork at JH for Main Clinical Trial : biomarkers and mechanisms	6-36 mo.	6-36 mo.

ANTICIPATED TARGET ENROLLMENT (QUARTERLY):

	Year 1				Year 2				Year 3				TOTAL
	Q1	Q2	Q3	Q4	Q1	Q2	Q3	Q4	Q1	Q2	Q3	Q4	
Target Enrollment Pilot Study	10	-	-	-	-	-	-	-	-	-	-	-	10
Target Enrollment Main Study (per quarter) (does not include the pilot study participants, who will not take part in the main study because they will no longer be sulforaphane naïve)	-	7	10	8	8	5	3	3	2	2	2	0	50

9) Study Endpoints*

a) *Primary study endpoint:*

- i) Ohio Autism Clinical Impressions Scale – Improvement (OACIS-I) Average Score.
- b) *Secondary study endpoints:*
- i) OACIS-I response rate (much or very much improved) on aberrant behaviors
 - ii) OACIS-I response rate (much or very much improved) on social communication
 - iii) Change in total ABC score (as well as subscales of Irritability, lethargy and social withdrawal, stereotypic behavior, hyperactivity and inappropriate language) from baseline

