Pilot Study to Determine Biomarkers: Prior to the main clinical trial, we will carry out a pilot study in 10 children with ASD, 6-12 years of age, who will receive sulforaphane, 2.2 micromoles/kg daily for 14 days. We will collect blood and urine samples before and at the end of treatment, in order to measure several parameters that are likely to demonstrate expected effects of sulforaphane, to standardize the assays and procedures, and to determine the most effective measures. Further details of the pilot study are discussed below.*

Study Design (Specific Aim 1): Following the pilot study for biomarkers, we will conduct a randomized, double-blind, placebo-controlled phase-2 clinical trial of sulforaphane in a single-arm crossover design in 3 phases, in 50 boys and girls (ages 3-12 years) with moderate to severe ASD (see Figure 1 below). In Phase 1 we shall treat participants for 15 weeks (50% with sulforaphane ((2.2 micromoles/kg body weight)), 50% with placebo of identical appearance). In Phase 2, all children will receive sulforaphane (2.2 micromoles/kg b.w.) on open label for an additional 15 weeks. In Phase 3 (6 weeks), participants will receive no sulforaphane, then return for followup at the end of the study. We project that treatment with sulforaphane will be associated with statistically significant improvements in physicians' global impressions, aberrant behaviors, social responsiveness and adaptive behaviors (see descriptions of outcome measures and statistical plan below).

Study variables will include clinician and parent assessments, and both clinical and scientific laboratory test measurements to evaluate for signs of toxicity and potential biomarkers of sulforaphane's effects. Our primary outcome measure will be the Ohio Autism Clinical Global Impression Scale (OACIS)^{27,28}. Secondary outcome measures will include the Aberrant Behavior Checklist (ABC)²⁵, Social Responsiveness Scale (SRS)²⁶, and Vineland Adaptive Behavior Scale (VABS)³⁰. The OACIS will be completed at each of 5 visits by clinicians; the ABC, SRS and VABS will be completed by the parents. All participants will have moderate to severe ASD, according to ADOS criteria as part of the screening process. Control subjects will be those children who

receive placebo for 15 weeks during Phase 1. All children will receive active sulforaphane during Phase 2.

[figure not shown]

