Visit	Informed consent, eligibility criteria (ADOS, Leiter-3)	Adverse event reporting	Medical history, vitals, physical exam	Autism symptom severity (OACIS-S, OACIS-I, ABC, SRS, Vineland Adaptive Behavior Scale)	Blood draw (LFTs, RFTs, TSH, CBC, HSP, mTor, Nerf), urine sample for isoprostanes	Study drug dispensing	Visit duration
Double blind phase (50% participants receive sulforaphane and 50% receive placebo)							
Screening/ baseline visit	X		X	X	X	8 weeks	~ 2.5 hours
3 week phone survey		X					~ 15 minutes

7 week visit		X	X	X	X	7 weeks	~ 1.5 hours
15 week visit		X	X	X	X	8 weeks	~ 1.5 hours
Open label phase (all participants receive sulforaphane)							
18 week phone survey		X					~ 15 minutes
22 week visit		X	X	X	X	7 weeks	~ 1.5 hours
30 week visit		X	X	X	X		~ 1.5 hours
36 week visit		X	X	X	X		~ 45 minutes

11) Data and Specimen Banking*

We plan to store leftover blood and urine samples in -80 C freezer in the Dept. of Pediatrics at UMass and the Cullman Chemoprotection Laboratory at Johns Hopkins for a period of 3 years after completion of the study. They will be accessed by the P.I. or study staff. The samples will continue to be de-identified and labeled with unique study I.D. numbers. The link between the study ID and identifiable information will only be accessible by the UMass personnel. At the end of 3 years the samples will be forever anonymized, and the link between study ID and identifiable information will be destroyed. We will make application to the IRB for any further studies to be conducted, by ourselves or others, using these specimens.

12) Data Management*

Statistical Analysis: The OACIS-I, SRS and ABC data will be analyzed in a mixed model ANOVA with fixed effects for visit, treatment group, and their interaction and random participant-specific intercepts. The effect of sulforaphane on mean change in OACIS-I, SRS and ABC total scores from baseline will be estimated using linear contrasts. Estimates will be unbiased if any loss to follow-up is missing at random, conditional on the observed data and our model assumptions. Significantly greater improvement from baseline in mean scores among participants randomized to sulforaphane based on a two-tailed test at $\alpha = 0.05$ will be taken as support of our primary hypothesis.

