A secondary analysis assessing proportion of participants in both groups who have responded to the study drug will be performed by Fisher's Exact test. This analysis will be done by categorizing the OACIS-I, SRS and ABC data. Participants will be considered as responders to study drug if they experience either of the following: they are much/very much improved (a score of 2 or less) on any subdomain of OACIS-I scale, their total ABC scores at 15 weeks decrease by at least 25% from baseline score, and their total SRS scores at 15 weeks decrease by at least 25% from their baseline score.

Biomarkers (testing mechanism of action of SFN) will be tested both as outcome variables in mixed model analyses and as predictors of differences in behavioral symptoms using the models described above for behavioral symptoms. Markers that both respond to sulforaphane treatment and predict differences in behavioral symptoms will be interpreted as possible mediators of any benefit from sulforaphane treatment. Safety of sulforaphane treatment will be assessed based on absolute rates of liver, thyroid and renal toxicity among participants treated with sulforaphane and based on comparison of the proportion of participants with such toxicities between the two treatment groups.

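### The section 12 success rule does not say which of three scales, or which visit, decides the primary hypothesis, and so does not match the single primary endpoint in section 9

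*Combined protocol and SAP*

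**What the plan says.** **Endpoint hierarchy.** Section 9 (Study Endpoints) lists a single primary endpoint, the scale identified as "Improvement (OACIS-I) Average Score". Change in total ABC and change in total SRS are secondary there. The Study Design text in section 10 repeats the ranking: OACIS is the primary outcome measure, and ABC, SRS and the Vineland scale are secondary.

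**Decision rule.** Section 12 (Data Management, Statistical Analysis) begins: "The OACIS-I, SRS and ABC data will be analyzed in a mixed model ANOVA". It continues: "The effect of sulforaphane on mean change in OACIS-I, SRS and ABC total scores from baseline will be estimated using linear contrasts". After a remark on missing data comes the success criterion. Significantly greater improvement from baseline in mean scores among those randomized to sulforaphane, two-tailed at 0.05, "will be taken as support of our primary hypothesis".

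**What is labelled secondary in section 12.** The label appears in the next paragraph, on the responder comparison: "A secondary analysis assessing proportion of participants in both groups who have responded to the study drug". The ABC and SRS mean-change contrasts do not carry it.

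**What the primary hypothesis is.** The term is not defined. Specific aim 1 in section 3 is worded as "To determine if there are measurable effects on social responsiveness and problem behaviors during treatment".

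**The concern.** The hierarchy and the decision rule are in different sections and do not fit together. The rule follows directly on contrasts for three scales, speaks of scores in the plural, and leaves open whether OACIS-I alone, any one scale, or all three must be significant. It also names no visit, although the model has visit and visit-by-treatment terms and there are blinded assessments at 7 and 15 weeks.

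Other wording in the document makes it harder to fall back on section 9. Aim 1 is phrased in terms of social responsiveness and problem behaviours, which are closer to SRS and ABC than to a clinician's global rating. Improvement from baseline is also natural language for ABC and SRS, whereas OACIS-I is itself a rating of change.

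The practical risk is a null OACIS-I result with a significant ABC or SRS. That is not far-fetched: section 4 reports differences on both parent scales in the earlier trial in adolescents and adults. Faced with that result, one reader of section 12 could report a failed primary hypothesis and another a supported one, and the choice could be made after seeing the data.

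**Working it through.** **Inputs**

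- Test level: two-tailed 0.05 (section 12). Only greater improvement on sulforaphane counts as support.
- Scales to which the rule could apply: three, OACIS-I, SRS and ABC (section 12).
- Correlation between the three test statistics: not given in the document. A common value r from 0 to 0.9 is assumed.

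**Step 1: the plan's own error rate.** For one scale at two-sided 0.05, the chance of a false claim in favour of sulforaphane is 0.05 / 2 = 0.025.

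**Step 2: readings that the sentence permits.**

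| Reading | Textual support | Chance of a false claim for sulforaphane |
|---|---|---|
| OACIS-I only | Sections 9 and 10 name it as primary | 2.5% |
| Any one of three | Shared model and contrasts, plural scores, no scale named | see step 3 |
| All three | Same sentence, read as a joint requirement | below 2.5% (0.16% at r = 0.5) |

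**Step 3: size under the any-one reading.** With independent scales the chance is 1 − 0.975³ = 1 − 0.9269 = 0.073.

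With a common correlation r and no true effect on any scale, the chance is 1 − ∫ φ(u) · Φ((1.96 − √r·u) / √(1 − r))³ du. Here φ and Φ are the standard normal density and distribution function. Numerical integration gives:

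| Assumed r | Any one of three, in favour of sulforaphane |
|---|---|
| 0 | 7.3% |
| 0.3 | 6.8% |
| 0.5 | 6.3% |
| 0.7 | 5.5% |
| 0.9 | 4.2% |

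Simulation of correlated normal test statistics agrees to within about 0.1 percentage point.

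**Step 4: the visit.** The rule names none. The Power Calculations in section 12 specify the OACIS-I, ABC and SRS differences at 15 weeks, and the ABC and SRS responder definitions also use 15 weeks. No success criterion or power statement is set at 7 weeks. The intended visit can therefore be inferred, but the rule should state it.

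**Step 5: what each way of closing the rule would cost.** With the planned 25 per arm and the plan's difference of 4 and SD of 4.9, the standardized effect is 4 / (4.9 × √(2/25)) = 2.886. OACIS-I power at two-sided 0.05 is then 82.3% (normal approximation) or 80.7% (t test). If any-of-three were kept with a Bonferroni level of 0.05 / 3 = 0.0167, 80% power would need 32 per arm for OACIS-I, 28 for ABC and 30 for SRS (normal approximation). Covering all three would take 2 × 32 = 64 participants, against 50 planned.

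**The case against.** The strongest reply is that the hierarchy is already fixed. Sections 9 and 10 both make OACIS the primary outcome and ABC and SRS secondary. In one combined document, the primary hypothesis most naturally attaches to the primary endpoint. On that reading a null OACIS-I is a failed primary whatever ABC and SRS show, and the stated error rate holds. This stands, and it is why the inflation is conditional. It does not remove the mismatch: section 12 is where success is defined, and nothing there limits the rule to OACIS-I.

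Three stronger readings are tempting, and the document does not support them.

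- A reader might infer that the plan adopts a rule under which each scale is tested at 0.05 and any one suffices. The sentence does not say so; it leaves that reading open along with two others.
- A reader might quote an error rate of 1 − 0.95³ = 14.3%, counting differences in either direction. The rule credits only greater improvement on sulforaphane, so that figure does not measure it.
- A reader might count the 7-week and 15-week contrasts as six chances of success. That adds a second unstated reading to the first, and the power section points to 15 weeks.

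It is also fair to say that a fixed test order for the secondary scales is a matter of preference in a phase I/II trial of 50 children.

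**Conclusion.** The point holds as a mismatch between the decision rule and the endpoint hierarchy. It does not show that the trial's error rate is inflated. If the rule is read as OACIS-I only, the chance of a false claim in favour of sulforaphane stays at 2.5%. If any one scale may decide, it is about 7.3% for independent scales, 6.3% at r = 0.5 and 4.2% at r = 0.9. These figures assume normal test statistics, a common correlation that the document does not supply, and no true effect on any scale. Independence is the upper end of the range shown; positive correlation is more plausible, since ABC and SRS are both completed by parents. The conclusion does not depend on the exact value, because the rate exceeds 2.5% throughout the range. The change should be made because the open rule leaves the verdict on a mixed result to be chosen after the fact.

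**What to change.** Replace the success sentence in section 12 with:

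> The primary hypothesis is supported only if the week-15 between-group contrast in OACIS-I average score favours sulforaphane at two-sided 0.05; the ABC and SRS mean-change contrasts are secondary and cannot by themselves support the primary hypothesis.

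This brings the rule into line with sections 9 and 10 and with the 15-week time point of the power section. The change should be made before treatment assignments are unblinded. A prespecified test order for ABC and SRS may be added but is not needed to close the gap.

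The cost is one sentence, with no added participants, visits or assessments. The sponsor gives up one thing: a significant ABC or SRS result alone could no longer be presented as support of the primary hypothesis.

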Power Calculations: We plan to enroll a total of 50 participants in the study, randomized 1:1 to sulforaphane and placebo. With OACIS-I, ABC, and SRS assessments at 0, 7 and 15 weeks our proposed design will have at least 80% power to detect significance in the following outcome measures if the following sample sizes are considered: **OACIS-I average Score:** With a total of 40 patients (20 on placebo and 20 on sulforaphane) entering this two-treatment parallel-design study, the probability is 80 percent that the study will detect a treatment difference at a two-sided 0.05 significance level, if the true difference of average OACIS-I score at 15 weeks between two treatments is 4 units. This is based on the assumption that the standard deviation of the average OACIS-I score is 4.9. **OACIS-I response rate on aberrant behaviors:** With a total of 44 patients (22 on placebo and 22 on sulforaphane) entering this two-treatment parallel-design study, there will be an 88% chance of detecting a significant difference at a two sided 0.05 significance level. This assumes that the response rate at 15 weeks of placebo is 9% and the response rate of sulforaphane is 54% on aberrant behavior subscale of OACIS-I. **OACIS-I response rate on social communication:** With a total of 44 patients (22 on placebo and 22 on sulforaphane) entering this two-treatment parallel-design study, there will be 82% chance of detecting a significant difference at a two sided 0.05 significance level. This assumes that the response rate of placebo is 7% and the response rate at 15 weeks of sulforaphane is 46% on the social communication subscale of OACIS-I. **Change in total ABC score from baseline:** With a total of 44 patients (22 on placebo and 22 on sulforaphane) entering this two-treatment parallel-design study, the probability is 81 percent that the study will detect a treatment difference at a two-sided 0.05 significance level, if the true difference of change in baseline of total ABC score at 15 weeks between the two treatments is 19.4 units. This is based on the assumption that the standard deviation of the change in ABC score is 22.1. **Change in total SRS score from baseline:** With a total of 48 patients (22 on placebo and 22 on sulforaphane) entering this two-treatment parallel-design study, the probability is 81 percent that the study will detect a treatment difference at a two-sided 0.05 significance level, if the true difference of change from baseline of total SRS score at 15 weeks between two treatments is 18.4 units. This is based on the assumption that the standard deviation of the change in SRS score is 22.0. Thus our proposed sample size of 50 participants, randomized 1:1 to sulforaphane and placebo will have more than enough power to detect significantly changes in majority of the outcomes listed above. The study will have 80% power to detect one or more toxicities expected to occur in at least 5.3% of sulforaphane-treated participants. The study is not powered to compare rates of safety outcome between sulforaphane and placebo treatment groups for a relevant non-inferiority threshold.

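### Naming Boschloo's exact test in place of Fisher's for the response-rate comparisons would be a free gain in power for a secondary analysis; the stated powers are not wrong.

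*Combined protocol and SAP*

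**What the plan says.** Section 12 (Data Management), Statistical Analysis, assigns the main hypothesis to a mixed model. It then adds: "A secondary analysis assessing proportion of participants in both groups who have responded to the study drug will be performed by" Fisher's exact test. The text continues: "This analysis will be done by categorizing the OACIS-I, SRS and ABC data". The ABC criterion is "their total ABC scores at 15 weeks decrease by at least 25% from baseline score", and the SRS criterion has the same form. For OACIS-I, a response is a rating of 2 or less on any subdomain.

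Section 9 lists two single-domain OACIS-I response rates, aberrant behaviors and social communication, as the first two secondary endpoints. Section 12, Power Calculations, gives each a power at 22 per arm:

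- **Aberrant behaviors:** "there will be an 88% chance of detecting a significant difference at a two sided 0.05 significance level", assuming "the response rate at 15 weeks of placebo is 9% and the response rate of sulforaphane is 54% on aberrant behavior subscale of OACIS-I".
- **Social communication:** "there will be 82% chance of detecting a significant difference at a two sided 0.05 significance level", assuming 7% on placebo and 46% on sulforaphane.

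Planned enrolment is 50 children, allocated 1:1. The power statements for ABC and SRS concern mean changes; the plan assumes no response rates for these two scales.

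**The concern.** The design fixes the two arm sizes. Fisher's test conditions on the total number of responders as well. With 22 to 25 children per arm this leaves few attainable p-values, and the true error falls below the declared 5%. The unused error could buy power without enrolling another child.

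A result near the boundary shows what is at stake. With 8/22 responders on sulforaphane and 2/22 on placebo, Fisher gives p = 0.069 and Boschloo p = 0.039. In a 50-child trial a named secondary endpoint could therefore miss significance because of the test chosen, although another exact test at the same level would have declared it.

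**Working it through.** **Inputs.** From Power Calculations: two-sided 0.05, 22 per arm, rates of 9% vs 54% and 7% vs 46%, and 25 per arm as the planned enrolment. From Background (section 4), the earlier adult trial: ABC responders 15/29 vs 2/15 and SRS responders 9/29 vs 0%. The last two pairs are used only to show a range.

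**Formulas.** For arms of size n1 and n2, list every table (a, b) and compute its two-sided Fisher p-value F(a,b).

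- Power of a rejection region R = sum over (a,b) in R of Bin(a; n1, p1) × Bin(b; n2, p2).
- True size of R = maximum over a common rate p of the same sum with p1 = p2 = p (grid of 1999 rates).
- Boschloo's p-value = maximum over p of P(F ≤ observed F). Its 5% region is the largest set of the form F ≤ c whose true size is at most 5%. Where Fisher's own size is below 5%, this set contains Fisher's region, so power cannot fall.

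**Step 1: reproduce the plan.** Fisher at 22 per arm gives 88.1% (stated 88%) and 81.3% (stated 82%). The uncorrected chi-square gives 93.2% and 88.6%, and the continuity-corrected normal formula 85.6% and 75.9%; neither matches both figures. The stated powers are therefore Fisher powers.

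**Step 2: one table by hand.** For 2/22 vs 8/22 there are 10 responders among 44. Fisher's p = 2 × [C(22,0)C(22,10) + C(22,1)C(22,9) + C(22,2)C(22,8)] / C(44,10) = 2 × (646,646 + 10,943,240 + 73,866,870) / 2,481,256,778 = 0.069. The maximum over p of P(F ≤ 0.069) is 0.039, which is Boschloo's p-value.

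**Step 3: true size of each test.**

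| Arms | Fisher, maximum | Fisher at a common rate of 10% | Boschloo, maximum |
|---|---|---|---|
| 22 + 22 | 2.44% | 1.4% | 4.97% |
| 25 + 25 | 3.28% | 0.9% | 4.63% |

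With arms that differ by one, Fisher's maximum is 3.7% (22/23), 4.0% (23/24) and 4.4% (24/25).

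**Step 4: power on the plan's OACIS-I rates, Fisher → Boschloo.**

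| Arms | 9% vs 54% | 7% vs 46% |
|---|---|---|
| 22 + 22 | 88.1% → 93.2% | 81.3% → 88.5% |
| 25 + 25 | 91.7% → 95.4% | 85.4% → 90.7% |

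The gain is about 5 and 7 points at 22 per arm and about 4 and 5 points at 25 per arm. In between it is smaller: 3.0 and 3.7 points at 23 + 23, and 2.7 and 3.4 at 24 + 24. With arms that differ by one it is about 1 to 3 points, for example 1.7 and 1.0 at 22/23.

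**Step 5: ABC and SRS, at the earlier trial's rates (an assumption, not the plan's).**

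- ABC (2/15 vs 15/29): 70.9% → 80.2% at 22 per arm and 77.2% → 84.8% at 25. Over equal arms of 22 to 25 the gain is about 6 to 9 points.
- SRS (0% vs 9/29): no gain at 22, 23 or 24 per arm (86.0% under both tests at 22), but 83.5% → 92.6% at 25. The jump comes from one table. 0/22 vs 5/22 has Fisher p = 2 × C(22,5)/C(44,5) = 0.0485 and is already significant; 0/25 vs 5/25 has p = 2 × C(25,5)/C(50,5) = 0.0502 and just misses, while Boschloo gives 0.033.

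**The case against.** The case for leaving the plan alone is fair. Fisher's test controls the type I error, it is widely understood, and conditional against unconditional testing is a recognised choice. The analysis is secondary, since the main hypothesis rests on the mixed model. The test, the sample size and the stated powers agree with one another, and both powers exceed 80%. All of this stands, and it limits the point to an optional improvement.

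A reader might be tempted to go further in four ways that the documents do not support:

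- **That the stated powers are wrong, or that power is lost against the plan.** The 88% and 82% are Fisher powers, so the conservatism is already counted in them. Any gain comes on top.
- **That the true error is at most half of 5% throughout.** That describes 22 + 22. At the planned 25 + 25 the maximum is about two thirds of 5%, and at 24/25 it is 4.4%.
- **That 5 to 7 points are available on every response rate.** That range belongs to the two OACIS-I rates at 22 + 22. Block randomization keeps the arms close in size, but dropout (4 of 44 in the earlier trial) can leave unequal evaluable arms, where 1 to 3 points is realistic. For ABC and SRS the plan gives no rates from which a gain could be claimed.
- **That the gain applies to the any-subdomain OACIS-I responder definition in Statistical Analysis.** No rate is given for it, so its gain cannot be computed. That Fisher's test also applies to the two single-domain endpoints is an inference. It rests on the reproduced powers, because the text does not say so outright.

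Nor may a result such as 8/22 vs 2/22 be called a true effect missed. It is a hypothetical table that shows where the two tests differ.

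**Conclusion.** The point holds as a free improvement to a secondary analysis, and not as an error in the plan. At the 22 per arm of the power section, Boschloo's test adds about 5 and 7 points for the two OACIS-I response rates; at the planned 25 per arm it adds about 4 and 5; with arms that differ by one it adds about 1 to 3. In none of the cases computed does it reduce power or exceed 5% true error.

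The figures assume independent binomial responses, the plan's own response rates, and the form of Boschloo's test that orders tables by the two-sided Fisher p-value. The ABC and SRS figures additionally borrow the earlier trial's rates in adolescents and adults, and show only how widely the gain can vary.

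**What to change.** Before unblinding:

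1. In section 12, Statistical Analysis, name Boschloo's exact unconditional test at two-sided 0.05 for the response-rate comparisons, and say explicitly that it covers the two single-domain OACIS-I endpoints of section 9.
2. Define the two-sided p-value as the one ordered by the two-sided Fisher p-value. Some software doubles a one-sided Boschloo p-value instead. The two agree in equal arms, but in unequal arms the doubled form can have less power than Fisher: with 23 and 22 evaluable children and SRS rates of 0% vs 9/29 it gives 86.0% against Fisher's 94.4%.
3. In section 12, Power Calculations, restate the two OACIS-I response-rate powers under that test: 93.2% and 88.5% at 22 per arm (95.4% and 90.7% at 25).
4. Report Fisher's p-value beside it as a sensitivity result.

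The cost is a sentence or two of analysis text and two restated figures. Patients, visits and data are unchanged.
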